**Table 6. A Mock Data Set**

Clinic Pair	1	2	3	4	5	6	7	8	9	10	11
Proportion Difference	.25	.10	.20	.50	.00	.25	.30	.40	.10	.30	.30

The standardized effect size is therefore  $0.25/0.20 = 1.25$ . Approximating the power of the permutation test by that of a paired t-test with 10 degrees of freedom, a sample size of 11 clinics per arm will yield a non-centrality parameter of  $1.25\sqrt{11} = 4.15$ , providing more than 95% power to detect a standardized effect size of 1.25 or more. The detectable effect size at 80% power is a mean difference 17.8 percentage points between eMPI and eUC practices. Even if the true standard deviation of the matched differences in proportions were as large as 0.281, we would still have 80% power to detect a 25 percentage point mean difference.

**Aim 2. To determine whether consistent use of eMPI leads to both short- and long-term improvements in clinical outcomes.** In this Aim, we will compare the change from baseline to each of the follow up (FU) time points (i.e., 3, 6, 9, and 12 months) in number of SFDs between eMPI and eUC patients using intent-to-treat principles. We will employ the generalized linear model (GLM) with identity link function for this comparison. The analysis model is of the form  $EY_{ij} = \alpha + \beta I_i + \sum \gamma_j T_{ij} + \sum \delta_j I_j T_{ij}$ , where for subject  $i$   $Y_{ij}$  is the number of SFDs for at time  $j$ ,  $I_i$  denotes group indicator for eMPI group (vs. eUC), and  $T_{ij}$  is the indicator for time at FU $j$  evaluation (vs. baseline). The regression coefficient  $\delta_j$  corresponding to the group-by-time interaction term estimates the difference in average change of SFDs at FU $j$  evaluation vs. baseline, comparing eMPI to eUC groups, and thus represents the effect of intervention on the SFDs. We will use generalized estimating equations (GEE) methodology to account for within-subject correlation due to multiple assessments for the same subject as well as the within-provider and within-practice correlations due to cluster sampling. We will also determine whether or not the corrective actions taken mediates the effect of intervention on outcomes; we will use the test of joint significance of the 2 paths involving a potential mediator, which best balance Type I error and statistical power. A variable  $M$  will be declared a mediator only if both the test of the regression coefficient of the explanatory factor  $X$  on the mediator and the test of the coefficient of the mediator on the outcome variable  $Y$  controlling for  $X$  are significant at level alpha = 0.05, 2-tailed. This approach allows for partial mediation which we fully expect to occur. In subsequent analyses we will estimate the indirect path effect with 95% confidence intervals using the asymmetric distribution of products method. Further exploration of causal mediation will

follow the methods of Imai et al. We will also examine whether the effect of intervention on SFDs is mediated by provider competencies, provider/caregiver communication or caregiver self-efficacy.

Missing data: Every effort to retain participants in the study will be exerted in order to avoid bias due to attrition. For those individuals who refuse continued participation, we will document reasons for study discontinuation and Rubin's multiple imputation method with 5 repeated imputations will be employed to impute the missing endpoint for conducting the intent-to-treat analysis.

**Power Analysis.** With a recruitment of 512 participants at baseline, we anticipate a final sample of 460 participants with complete data for the primary analysis assuming no more than 10% attrition at 12 month evaluation. This estimate of attrition rate is conservative based on our prior experience. To account for the intra-cluster correlation due to cluster sampling, we estimate that an intra-provider correlation coefficient is no greater than 0.03 from our prior studies. Although the intra-practice correlation coefficient should be smaller than intra-provider correlation coefficient, we conservatively used the same value (i.e., 0.03). Under the above assumption, with 230 participants per group, we will be able to provide 80% power to detect a standardized effect size of  $\geq 0.29$  in change of number of SFDs. Even if actual attrition is greater than we expect (e.g., 15%), the detectable standardized effect size will only increase slightly to 0.30. Further, as we will impute missing data using informative covariates for the primary analyses, the power to detect such effects will be  $>80\%$ .

**Aim 3. To evaluate the process of program implementation:** In order to evaluate the potential for dissemination of this primary care intervention, we will report specific summary measures recommended by the RE-AIM framework. We will compare the provider-level proportion of visits with corrective actions taken by the eMPI providers to that of eUC providers using the same analytic approach stated in Aim 2 (Reach). We will evaluate the impact of eMPI on guideline-based corrective actions and symptoms (*Effectiveness*). We will qualitatively describe problem solving progress that occurs in each practice as part of process of improvement, by coding the specific barriers that arise during implementation and are collected by clinic champions, and the solutions that eMPI practices identify (*Adoption*). We will report consistency with which participants in the intervention arm receive the protocol through EHR data, practice observations of the process of implementation and data collected from OW contacts with participants. Additional measures of implementation of eMPI include 1) caregivers' completion of severity/control assessments at the visit; 2) provider and caregiver receipt of prompts; 3) providers' documentation of asthma discussion (*Implementation*). We will use provider survey responses to evaluate the extent to which each intervention component was continued or modified post-study and sustained effects on the primary outcome (*Maintenance*). Using EHR records of 5,000 children across all four waves of translation, we will determine if eMPI practices will (a) reach successively higher levels of guideline-based care, (b) achieve that level more quickly, and (c) sustain use of guidelines for 18 months. The analytic approach to address this will involve a statistical model with the main effect of intervention condition, time (which represents the level of Implementation), and the indicators of waves (which will allow us to evaluate sustainability), plus all the two-way and three-way interactions. We expect to see specific three-way interaction effects involving trends in rates of guideline-based care over 24 months, with an ever steeper linear increases and less pronounced downturns seen from wave to wave, in eMPI practices vs. eUC. Guideline-based care is intended to ensure that children receive needed services in a more timely fashion. We will examine patterns of utilization by children in both groups using the EHR, including adherence to clinic visits, specialty referrals, emergency and in-patient care, and OW referrals.

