## B. Subjects and Setting

Outpatient practices (n=22) that are part of Montefiore Health System will participate in the study (see Letter of Support). These 22 practices are located throughout the Bronx, NY, represent different practice types, and have participated in several of our prior studies (Table 3). Though there were initially 22 proposed outpatient practices, two practices were closed, two practices (FCC-B and FCC-C) were combined as a single site given that they serve patients in the same facility, and one practice was excluded given no pairing available, resulting in a total n=18 participating outpatient practices. The number of children with asthma across practices (N=10,109) of whom we estimate ~ 50% (N=5,000) to have persistent or uncontrolled asthma is sufficient to meet our sample size needs. A subset of 512 children will be recruited over 4 years (~128 participants each year) to obtain clinical outcomes data that are not in the EHR.

Table 1. Primary Care Practices*					
Site	Practice Type	Provider Type	# 2-12yr olds in practice	# 2-12yr olds with asthma	# visits for 2-12yr olds with asthma
Astor Avenue	NHC	Pediatrics	3,075	576	1,012
Bronx East	NHC	Pediatrics	4,775	884	1,516
Burke Avenue	NHC	Pediatrics/Family MD	1,102	117	196
Castle Hill	FQHC	Family MD	814	97	135
CFCC	FQHC	Pediatrics	5,791	1,144	1,824
CHCC	FQHC	Pediatrics	4,658	1,332	2,488
Co-op Bartow Ave	NHC	Pediatrics	2,485	634	1,059
Eastchester	NHC	Pediatrics	1,350	325	703
FCC - B	Hospital Clinic	Pediatrics	3,671	684	1,028
FCC - C	Hospital Clinic	Pediatrics	3,470	805	1,300
FHC	FQHC	Family MD	1,739	339	606
Grand Concourse	NHC	Pediatrics/Family MD	3,133	540	868
Grand UCC	NHC	Pediatrics/Family MD	2,950	235	262
HIP Cross County	NHC	Pediatrics/Family MD	3,058	272	385
MAP-8	Hospital Clinic	Pediatrics	2,935	631	1,551
Marble Hill	NHC	Pediatrics/Family MD	1,143	186	294
University Avenue	FQHC	Pediatrics/Family MD	1,697	344	645
Verde Clinic	NHC	Family MD	359	78	146
Wakefield	NHC	Pediatrics	354	309	600
West Farms	FQHC	Family MD	954	215	368
White Plains Road	NHC	Pediatrics/Family MD	1,204	174	273
Williamsbridge	FQHC	Family MD	1,059	188	308
TOTAL	-	-	51,776	10,109	17,567

FQHC=Federally Qualified Health Center; NHC=Neighborhood Health Center. \*Number of patients seen between 1/1/14-12/31/14

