### **Aim 1. To test the impact of eMPI on provider adoption of asthma management guidelines.**

The **primary outcome** is a clinic-level variable measured by the ratio of number of visits with  $\geq 1$  guideline-based corrective actions to the number of visits by patients aged 2-12 years with persistent or uncontrolled asthma at the time of visit. The **primary null hypothesis** is that there is no difference between eMPI and eUC clinics in the mean proportion of visits where the necessary corrective actions were taken. To test this null hypothesis, we will use a matched-pairs randomization (or permutation test) at the 0.05 two-tailed level of

significance. The permutation test will account for the fact that clinics (rather than providers) are randomized and that the randomization will be performed within clinic pairs. Each pair of clinics will produce a matched difference in the proportions of corrective actions, and under  $H_0$  the randomization can be viewed as attaching a random plus or minus sign. Thus there will be  $2^{11} = 2,048$  possible signed permutations, allowing a two-tailed p-value as significant as  $2/2,048 < 0.001$  (if all 11 pairs show a greater proportion of corrective actions taken by the eMPI practices). Assuming no important practice characteristics are significantly out of balance (at two-tailed  $p < 0.01$ ), the permutation test will comprise the primary analysis. If any important clinic characteristics are significantly imbalanced at  $p < 0.01$ , we will adjust for such variables in a linear regression model and report the adjusted intervention coefficient as the primary result. We will also examine for a clinic-size (or provider-type) by intervention interaction. If not significant at the 5% level, the above approach will be used to provide the primary results. If significant, we will attempt to identify factors that affect the primary outcomes and might differ between clinics (or provider types). If including such factors removes the interaction, we will quote the adjusted intervention effect from the model including such factors. If not, we will quote two intervention effects (for large and small clinics) leaving the interaction unresolved.

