**Power Analysis.** We conservatively estimate that the mean difference between eMPI and eUC clinics in the proportion of visits where the necessary corrective actions were taken will be at least 25 percentage points. To express this as a standardized effect size, we assume the standard deviation of the paired differences in the proportion of corrective actions will be no more than 0.2, based on several mock data sets generated by the investigators reflecting their clinical experience and best estimates. We present one generated data set in Table 6 for illustration. This hypothetical data set has an average matched difference in proportions of 0.246 (about 25 percentage points) with standard deviation 0.142 (14.2 percentage points). Our assumption of a standard deviation of 0.2 or 20 percentage points is thus about 50% larger than in this illustrative example.

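### The primary power statement and permutation count use 11 clinic pairs, but 18 practices (9 pairs) take part: power is about 90%, not above 95%, and two companion figures are wrong even for 11 pairs.

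*Combined protocol and SAP*

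**What the plan says.** Under Aim 1 of the Summary of Analytic Plan, the primary analysis is a matched-pairs permutation test "at the 0.05 two-tailed level of" significance, with clinics randomized within pairs. The text counts 2^11 = 2,048 sign permutations and a smallest two-tailed p-value of 2/2,048, reached "if all 11 pairs show a greater proportion of corrective actions taken by the eMPI practices".

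The Power Analysis that follows expects a mean difference that "will be at least 25 percentage points". For the spread, "we assume the standard deviation of the paired differences in the proportion of corrective actions will be no more than 0.2", a value taken from mock data sets made by the investigators. The calculation then reads: "Approximating the power of the permutation test by that of a paired t-test with 10 degrees of freedom, a sample size of 11 clinics", with non-centrality 4.15 and power above 95%. Two further figures follow. One is the smallest detectable effect: "The detectable effect size at 80% power is a mean difference 17.8 percentage points between eMPI and eUC practices". The other is a robustness claim for a 25-point difference: "Even if the true standard deviation of the matched differences in proportions were as large as 0.281, we would still have 80% power".

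Section B, Subjects and Setting, says that of the 22 practices proposed, two closed, two were combined into one site, and one was dropped because no partner was available, "resulting in a total n=18 participating outpatient practices". The Design Overview and the Randomization paragraph still describe 11 pairs.

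**The concern.** Randomization and the primary test both work within pairs, so the number of pairs fixes the permutation set, the degrees of freedom and the power. The current text gives 18 practices in one place and 11 pairs in the analysis, and nowhere recalculates power for 18.

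The robustness claim matters most. The assumed standard deviation of 0.20 rests on mock data, not on observed clinic differences. The plan tells readers that it could be about 40% too low (0.281/0.20 = 1.405) before power falls to 80%. If that margin is wrong, a reader of the protocol will credit the primary comparison with more tolerance, and more ability to detect modest effects, than it has.

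**Working it through.** **Inputs.** Mean paired difference 0.25 and SD of paired differences 0.20 (Aim 1, Power Analysis); two-sided alpha 0.05 (Aim 1); 11 pairs and 10 df (Power Analysis, text under Table 6); 18 practices (section B).

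**Number of pairs.** 22 − 2 (closed) − 1 (two sites merged into one) − 1 (no partner) = 18, and 18/2 = 9. The documents never print 9 pairs. It is inferred from the count and from the reason given for the last exclusion.

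**Method.** This is the plan's own approximation. For n pairs, df = n − 1 and non-centrality = (difference/SD) × √n. Power is the probability that a non-central t variable falls beyond ± the 97.5% t quantile. The 80% figures come from solving for the standardized effect d that gives power 0.80; then detectable difference = 0.20 × d and tolerable SD = 0.25/d.

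**Reproducing the plan with 11 pairs (10 df).**
- Non-centrality: 1.25 × √11 = 4.146. The plan's 4.15 is right.
- Power: 96.1%. The plan's figure of more than 95% is right for 11 pairs.
- 80% power needs d = 0.9377. Detectable difference = 0.20 × 0.9377 = 18.8 points (printed: 17.8). Tolerable SD = 0.25/0.9377 = 0.267 (printed: 0.281).
- At the printed values, d = 0.178/0.20 = 0.89, or 0.25/0.281 = 0.89. Power is 75.8%, not 80%.

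Other approximations with 11 pairs do not recover the printed values. A normal approximation gives 16.9 points and 0.296, a one-sided t gives 16.1 and 0.310, and sums of t and normal quantiles, or of two t quantiles, give 18.5 to 18.7 and 0.270 to 0.267. The printed values agree numerically with 12 pairs and 11 df (17.77 points, 0.2813) and with 11 pairs and 20 df (17.76 points, 0.2815). Neither is the stated design, and the documents do not show how the figures arose.

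**The same calculation with 9 pairs (8 df).**
- Non-centrality: 1.25 × √9 = 3.75.
- Power at 25 points with SD 0.20: 90.6%.
- 80% power needs d = 1.067. Detectable difference = 0.20 × 1.067 = 21.3 points. Tolerable SD = 0.25/1.067 = 0.234.
- Sign permutations: 2^9 = 512. Smallest two-sided p = 2/512 = 0.0039. Two-sided p-values move in steps of 2/512, so the largest attainable level not above 0.05 is 24/512 = 0.047.

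| Quantity | Printed | 11 pairs, 10 df | 9 pairs, 8 df |
|---|---|---|---|
| Non-centrality | 4.15 | 4.15 | 3.75 |
| Power, 25 points, SD 0.20 | >95% | 96.1% | 90.6% |
| Detectable difference, 80% power | 17.8 points | 18.8 points | 21.3 points |
| Tolerable SD, 25 points, 80% power | 0.281 | 0.267 | 0.234 |
| Sign permutations | 2,048 | 2,048 | 512 |
| Smallest two-sided p | <0.001 | 0.00098 | 0.0039 |

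**Check against the test itself.** Simulating the exact sign-flip test on normally distributed differences gave about 96% power for 11 pairs and 89% to 90% for 9 pairs at 25 points and SD 0.20 (two runs, 8,000 and 20,000 replicates). The t approximation is adequate here.

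**The case against.** The strongest reply is that little of consequence changes. On the plan's own assumptions power is still about 90%, well above 80%. A smallest p of 0.0039 leaves the 0.05 threshold within reach. The permutation test is defined by sign flips within pairs, so it remains valid with 9 pairs without any new rule. The loss of practices is openly reported, the headline power was right for 11 pairs, and a null result should in any case be read from the estimate and its interval rather than from planning power. All of this stands, and it means that the trial should not be called underpowered.

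It does not rescue the printed figures. The reduction to 18 practices is in the current text, while the description of the primary test and its power still assumes 11 pairs. Calling the numbers planning history does not help with 17.8 points and 0.281, which were already wrong for the planned design.

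Two cautions also stand. Nine pairs is an inference, though a firm one, and the text does not say when the closures and merger happened relative to randomization. Nine-pair power at the two printed 80% points is about 65%, but that combines the lost pairs with the arithmetic slip. It is not the power at the planned effect and should not be quoted without the 90.6%.

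**Conclusion.** The concern holds. There are two separate errors.

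1. **Outdated pair count.** With 9 pairs, power for the planned effect is 90.6%, so the chance of missing it rises from 3.9% (11 pairs) to 9.4%. The margin on the standard deviation is 17% above the assumed 0.20 (0.234/0.20 = 1.17), against the 40% that the plan advertises.
2. **Arithmetic slip independent of the lost clinics.** For 11 pairs and 10 df, the detectable difference is understated by about 1 point and the tolerable standard deviation overstated by about 0.014. Power at the printed values is about 76%, not 80%.

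These results rest on 18 practices forming 9 complete pairs, on the plan's difference and standard deviation, and on its paired-t approximation. The validity of the permutation test is unaffected.

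**What to change.** In Aim 1 and its Power Analysis, restate the primary test for 9 pairs:

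- 512 sign permutations and a smallest two-sided p of 0.0039;
- 8 degrees of freedom and non-centrality 3.75;
- about 90% power for 25 points at a standard deviation of 0.20;
- a detectable difference of 21.3 points at 80% power;
- a tolerable standard deviation of 0.234.

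If the 11-pair figures are kept as the planning basis, put them in a dated note and correct them to 18.8 points and 0.267. State the number of pairs explicitly in section B, together with when the closures and merger occurred relative to randomization. Bring the Design Overview, Randomization, Screening and Compensation text, which still refers to 11 pairs or 22 practices, into line.

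The cost is wording and figures only. The stated power becomes somewhat less favourable. No additional clinics and no change to the test are needed.

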## Study Overview

### A. Study Design

**Design Overview:** We will conduct a 2-group cluster randomized trial comparing eMPI to enhanced usual care (eUC) in 22 Bronx practices serving over 10,000 children with asthma. The randomization will be at the practice level to avoid contamination. Each practice will be matched into 11 similar pairs based on size and type and then randomly assigned to either eMPI or eUC.

Provider adoption of guidelines and utilization of care in all patients (~5,000) ages 2-12 years with persistent or uncontrolled asthma from eMPI and eUC practices will be evaluated using EHR data and practice-based screening for asthma severity and control. We will also enroll a random subset of 512

caregivers of children with persistent/uncontrolled asthma from both study arms to systematically evaluate caregiver-reported child morbidity outcomes and obtain measures not available in EHR. These children will be enrolled at the time of the office visit and followed prospectively for 4 time points - 3, 6, 9, and 12 months after the initial visit - to assess clinical and process-focused outcomes.

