Enrollment goals for each practice will be based on the number of children with asthma seen at the practice. Since enrollment will occur over an extended time period, we will block enrollment by site pair to assure an equal balance of children in each group for each seasonal time period. Research staff will be present in each clinic 2-3 days/week for recruitment, until monthly enrollment goals are met for that practice. We will review the practice's schedule the day before to determine if potentially eligible participants are scheduled for a visit. Research staff will call patients with asthma ages 2-12 years and ask families to come to their appointment with physician 30-60 minutes earlier to be screened by the nursing staff for asthma severity. If eligible, the caregiver/child will be informed about the study, undergo the informed consent process and complete baseline survey prior to seeing the physician. Recruitment goals will be reviewed weekly for each practice and adjustments of staffing made as needed. Days for recruitment will vary to ensure that patients of providers who are in clinic on certain days of the week are not over- or under-sampled (see Recruitment Protocol, Appendix A). Following informed consent/assent, research staff will conduct a 10-minute survey with the primary caregiver in the waiting room to obtain *baseline measures* of enrolled participants. All survey instruments will be available in English/Spanish and questions will be read aloud. Caregivers will be offered a private location within the waiting room to complete the survey. The baseline measures include standard demographic and health history variables, healthcare utilization, quality of life, beliefs about medication and adherence (Appendix A).

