**eMPI Intervention:** The eMPI components are described in Table 4 and closely mirror implementation strategies recommended by the panel of experts in implementation science for development of a tailored multilevel strategy for implementation. First, at every office visit, caregivers of children ages 2-12 years with persistent or uncontrolled asthma will be asked to complete a screening survey in EPIC Electronic Health Record (EHR) during the triage portion of their doctor visit (Appendix A). Clinic staff will review the answers with the caregiver and read the questions aloud as needed. Based on these responses, a prompt for both the provider and caregiver will be generated in EPIC EHR using a simple algorithm (Appendix B). The *provider prompt* will be delivered to the provider at each visit via EHR and include information on child's current level of asthma severity or control, controller

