
TABLE 4. CORE ELEMENTS OF eMPI MULTI-LEVEL TRANSLATIONAL STRATEGIES

- Direct Support for Providers' Delivery of Guideline-Based Care in Practice**
  - Caregiver waiting room assessment of asthma severity and control
  - Provider prompts to deliver guideline-based corrective actions at every visit
  - Caregiver prompts to encourage discussion with provider
- Enhancements to Increase the Feasibility and Sustainability of eMPI**
  - Waiting room assessment for the prompts on Tablet PCs
  - Physician prompts in Electronic Health Record (EHR)
- Involving Clinic Staff in Promoting and Supporting Use of Guidelines**
  - Regular staff administer and survey information for prompts
  - Outreach Worker-delivered care coordination and support to ensure recommendations are followed by patients
- Building Accountability and Commitment to Guideline-Based Care**
  - Designation of clinic champion to lead practice change
  - Designation of Practice Advisory Board to monitor and guide change
- Promoting Providers' Understanding, Acceptance and Use of Guidelines**
  - Interactive seminars about asthma guidelines, pocket cards with guidelines
  - Ongoing feedback about performance improvement
  - Identification of barriers to guideline use and eMPI implementation
  - Ongoing sharing of best ideas and solutions to overcome barriers

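### The symptom-free-day effect is an unadjusted difference in change; adjusting for the baseline value already collected would usually be more precise at little cost

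*Combined protocol and SAP*

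**What the plan says.** The Aim 2 analysis states that "we will compare the change from baseline to each of the follow up (FU) time points". The model for SFDs has an arm term, an indicator for each follow-up time, and arm-by-time interactions, fitted by GEE with clustering by child, provider and practice. Baseline SFD is an outcome row, not a covariate, and the arm term leaves the baseline difference unconstrained. Each interaction coefficient is described as "comparing eMPI to eUC groups, and thus represents the effect of intervention on the SFDs". The model contains no covariates. The Aim 2 power paragraph mentions informative covariates only for imputing missing data.

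On timing, Study Design says "These children will be enrolled at the time of the office visit and followed prospectively for 4 time points". The enrolment procedures for the subset of 512 say "Research staff will be present in each clinic 2-3 days/week for recruitment, until monthly enrollment goals are met for that practice", and that eligible families "undergo the informed consent process and complete baseline survey prior to seeing the physician". The eMPI Intervention section says that "at every office visit, caregivers of children ages 2-12 years with persistent or uncontrolled asthma will be asked to complete a screening survey", and Table 4 lists "Provider prompts to deliver guideline-based corrective actions at every visit". The inclusion, exclusion and enrolment text does not require the enrolment visit to be the child's first after the practice starts eMPI.

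**The concern.** SFD change is the main clinical outcome. A change score fixes the coefficient on baseline at 1. When the correlation between baseline and follow-up is moderate and the SDs are similar, the best coefficient is below 1, and the change score carries avoidable noise. Baseline SFD is measured on every enrolled child, so adjusting for it needs no new data.

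The secondary issue is what the baseline represents. A survey taken before the physician contact protects a child enrolled at the first eMPI visit. It does not protect a child whose provider was already prompted at an earlier visit. Any benefit already present at that child's baseline would be subtracted from the estimated change, and the Aim 2 report would not show how many children this affects.

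**Working it through.** **The plan's figure.** The Aim 2 power paragraph gives a detectable standardized effect of 0.29 in change of SFDs (80% power, 230 per arm, ICC 0.03). With d = (1.96 + 0.84)·√(2·DEFF/230) and DEFF = 1 + (m − 1)·0.03, the result is 0.266 for about 200 providers (m = 2.3), 0.330 for 22 practices (m = 20.9) and 0.344 for 18 practices (m = 25.6). The 0.29 does not follow from these cluster counts. That is a separate matter. The comparison below is a ratio of variances and does not use 0.29.

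**What the planned coefficient is.** On simulated complete data, the arm-by-time coefficients from GEE (independence and exchangeable working correlation) equalled the raw differences in mean change to all printed digits.

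**Inputs from the documents.** 460 analysed children and ICC 0.03 (Aim 2 power paragraph); K = 18 participating practices, 22 originally (Subjects and Setting). The ICC is read here as that of SFDs at one time point.

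**Assumed inputs.** Child-level correlation ρ between baseline and follow-up, 0.3 to 0.7; practice autocorrelation c, 0.5 to 1; ratio λ of baseline SD to follow-up SD, 1 or 0.7; equal practice sizes, m = 460/K.

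**Formulas, per practice mean, follow-up variance 1.**
- V1 = ICC + (1 − ICC)/m
- V0 = λ²·V1
- C = λ·[c·ICC + (ρ − c·ICC)/m]
- Change score: V1 + V0 − 2C
- Adjusted for child and practice-mean baseline: (V1 − C²/V0)·[1 + 1/(K − 4)], where the last factor charges one practice-level degree of freedom

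**One case in full.** K = 18, ρ = 0.5, c = 0.75, λ = 1:
- m = 25.56; V1 = V0 = 0.03 + 0.97/25.56 = 0.0680
- C = 0.0225 + (0.5 − 0.0225)/25.56 = 0.0412
- Change score: 2 × (0.0680 − 0.0412) = 0.0535 (unrounded inputs)
- Adjusted: (0.0680 − 0.0412²/0.0680) × 15/14 = 0.0430 × 1.071 = 0.0461
- Ratio: 0.0535/0.0461 = 1.16

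With λ = 0.7, V0 = 0.0333 and C = 0.0288. The change-score variance is 0.0680 + 0.0333 − 0.0577 = 0.0436, the adjusted variance stays 0.0461, and the ratio is 0.95.

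**Range of change-score to adjusted variance.**

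| Setting | Equal SDs | Baseline SD 0.7 of follow-up |
|---|---|---|
| ICC 0.03, as above | 1.02–1.38 | 0.93–1.06 |
| Same, analysis respecting pairs (n = 9 or 11, factor 1 + 1/(n − 3)) | 0.94–1.29 | 0.86–1.00 |

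At ICC 0.10 and equal SDs, without pairs, the range is 0.98–1.32.

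The lower limits have a simple source. Before the degree-of-freedom charge, the adjusted variance is never larger than the change-score variance. The worst case is therefore the charge itself: 14/15 = 0.93 at 18 practices, or 6/7 = 0.86 at 9 pairs.

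**In standard errors, ICC 0.03, no pairs.** At equal SDs, 1/√1.02 = 0.99 and 1/√1.38 = 0.85, so the adjusted standard error is about 1% to 15% smaller. At λ = 0.7, 1/√1.06 = 0.97 and 1/√0.93 = 1.04, so it runs from 3% smaller to 4% larger.

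**Does adjustment also repair an exposed baseline?** The fraction of any such dilution left in the adjusted estimate is C/V0: 0.37 to 0.83 at equal SDs, and 0.54 to 1.18 at λ = 0.7. It can exceed 1, so adjustment is not a remedy.

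**The case against.** The planned estimator is valid, and the ratios cross 1, so one can call this a preference. Eligibility mostly selects children with frequent recent symptoms, and SFDs are counted over two weeks, so a smaller baseline SD is plausible. The correlations and the SD ratio are not in the documents. Practice sizes are also unequal: enrolment goals follow asthma volume, and Table 1 runs from 78 to 1,332 children with asthma. Proportional allocation of 460 over the listed 10,109 gives about 4 to 61 per practice, so some practice means would be noisy. The 7% worst case holds only for the setting computed. All of this stands. It limits the claim to a likely gain.

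On timing, Study Design counts follow-up from an initial visit, and the outreach-worker text contrasts that visit with later ones. This suggests, without stating it, that enrolment was conceived as a first visit.

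A reader might infer three stronger things that the documents do not support:

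- **That a definite share of the effect is lost.** Neither the share of eMPI children with an earlier prompted visit nor the effect present at baseline is given. The Background says one prompted visit brought short-term but no long-term clinical gain, and eligibility tends to exclude children who have already improved. Dilution near zero is possible.
- **That the exposure history is already collected.** Prompt data sit in each patient's record, but office visits of the 512 are reviewed at the follow-ups, and the waiver extract is clinic-level. Nothing commits to extracting visits before enrolment.
- **That visits are not linked to SFDs at all.** The mediation analysis links corrective actions to SFDs. Only exposure before baseline is left out.

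**Conclusion.** The concern holds as a low-cost improvement, not as an error. The planned SFD effect is an unadjusted difference in change. Adjusting for baseline would probably give a tighter estimate: variance ratio 1.02 to 1.38 at equal SDs, but 0.93 to 1.06 if the baseline SD is 0.7 of follow-up. These figures rest on 460 children, 18 to 22 equal practices, ICC 0.03 and the assumed correlations. The possible efficiency loss is about 7% in this setting, and about 14% if the analysis also respected pairs.

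The gap in enrolment timing is real in the text, but no loss can be stated for it.

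**What to change.** 1. Model SFDs at 3, 6, 9 and 12 months on arm-by-time, with the child's baseline SFD and the practice-mean baseline SFD as covariates. Keep the planned GEE clustering, and keep the current change-score model as a sensitivity analysis. The cost is SAP wording, one practice-level degree of freedom, and the possible small efficiency loss given above.
2. State whether a child may enrol after an earlier eMPI visit. If visit history before enrolment can be taken from the records of the consented 512, report by arm the share with a visit between practice start and baseline, as description only. This is an added extraction, and the sponsor should confirm that the consent covers it. Present the baseline covariates as a precision measure, not as an answer to this second point.
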